RBC	Red blood cell
RCD-II	Type II Refractory Celiac Disease
RE	Role limitations due to emotional problems
SAE	Serious adverse event
SAP	Statistical analysis plan
SC	Subcutaneous
sCD3-	Surface CD3-negative
sCD8-	Surface CD8-negative
SD	Standard deviation
SOC	System organ class
ULOQ	Upper limit of quantification
UN	Unstructured
VT	Vitality
VH:CD	Villous height to crypt depth ratio

WBC White blood cell

WHO DD World Health Organization Drug Dictionary

1 Introduction

This is a statistical analysis plan (SAP) for study CELIM-NRCD-001 which is based on the final study protocol CELIM-NRCD-001 Version 3 (dated 29AUG2016). This SAP describes the statistical analyses which will be presented in the clinical study report.

2 Study objectives

The study objectives are the following:

The **primary objective** of the study is:

- To assess the efficacy of AMG 714 in attenuating the effects of gluten exposure in adults with celiac disease.

The **primary efficacy endpoint** is:

- Attenuation of gluten-induced small intestinal mucosal morphological injury, measured morphometrically as villous height to crypt depth (VH:CD) ratio.

The primary endpoint of the study is the difference in the Baseline-to-Week-12 % change of VH:CD ratio between each of the two AMG 714 dose arms against the placebo arm.

The **secondary efficacy endpoints** of the study are:

- Attenuation of gluten-induced small intestinal mucosal inflammation measured as intraepithelial lymphocyte (IELs) density;
- Attenuation of gluten-induced small intestinal mucosal morphological injury using a grouped classification of Marsh score;
- Attenuation of gluten-induced serum antibodies (i.e. anti-tissue transglutaminase antibodies [anti-tTG] IgA, anti-deamidated gliadin peptide antibodies [anti-DGP] IgA and IgG);
- Attenuation of gluten-induced clinical symptoms (i.e. Bristol Stool Form Scale [BSFS], Gastrointestinal Symptom Rating Scale [GSRS] and celiac disease GSRS [CeD-GSRS]).

The secondary endpoints of Marsh score and total IEL counts will be evaluated by the change from baseline to Week 12 between the two AMG 714 dose arms and the placebo arm. Anti-tTG IgA, anti-DGP IgA and IgG will be evaluated by comparing the change from baseline in results obtained after every four weeks of two AMG 714 dose arms and placebo arm. BSFS, GSRS and CeD-GSRS will be evaluated by comparing the change from baseline in weekly scores of two AMG 714 dose arms and placebo arm.

The **secondary objective** of the study is:

- To assess the safety and tolerability of AMG 714 when administered to adult patients with celiac disease exposed to a gluten challenge.

The **safety endpoints** of the study are:

- Adverse events (AEs);
- Clinical laboratory tests;
- Physical examination;
- Vital signs;
- Immunogenicity.

Clinical laboratory tests -including immunogenicity-, physical examinations and vital signs will be tabulated by time point and treatment group and reviewed for potential safety signals. All adverse events (AEs) and serious adverse events (SAEs) will be listed and tabulated by treatment group, system organ class (SOC), preferred term (PT) and further by severity and relatedness to the study drug.

The **exploratory objectives** of the study are:

- To assess the pharmacokinetics (PK), pharmacodynamics (PD), and PK/PD associations of AMG 714.

The **exploratory endpoints** of the study are:

- PK;
- PD, including
 - Physician Global Assessment of Disease (PGA);
 - Biomarkers of disease activity;
 - Celiac Disease Patient-Reported Outcome (CeD PRO);
- Exposure/Response (PK/PD).

PK data will be tabulated by treatment group. In addition, dose proportionality, achievement of steady-state, and accumulation ratio based on C_{trough} concentrations, comparison of C_{trough} levels with corresponding values in study 20060349, and correlation of C_{trough} concentrations with biomarkers of disease activity will be evaluated. Exploratory PD endpoints are Physician Global Assessment of Disease (PGA), biomarkers of disease activity (i.e., CRP, serum IL-15 [sIL-15]) and Celiac Disease Patient Reported Outcome (CeD PRO). The exploratory PD endpoints will be evaluated by investigating the change from baseline and weekly scores, if applicable, of AMG 714 dose arms and placebo arm. PK/PD association will mainly be assessed graphically.

PK analyses will be described in detail in a separate PK Data Analysis Plan (DAP) to be prepared by Celimmune.

In subjects with dermatitis herpetiformis (DH), optional photography will be conducted according to the study manual. Skin biopsies will be allowed per investigator's discretion but will not be part of this protocol. Any skin information on DH will be summarized by Celimmune for descriptive purposes without formal statistical analysis.

3 Study type and design

CELIM-NRCD-001 is designed to be a Phase 2a randomized, double-blind, placebo-controlled, parallel-group study to evaluate the efficacy and safety of AMG 714 for the attenuation of the effects of gluten exposure in adult patients with celiac disease during a gluten challenge.

After signing consent subjects will be screened for the study. All subjects who meet the study entry criteria will be randomized at a 1:1:1 ratio to receive 150 mg or 300 mg AMG 714 or placebo once every two weeks for 10 weeks. Randomization will be stratified by site and sex. The study drug (AMG 714 or placebo) will be administered at the clinical site in a double-blind fashion via subcutaneous (SC) injection. Subjects will remain confined to the study site for a minimum of 1 hour after each administration of study medication. During this time the Investigator and study site staff will assess the subject for AEs and collect the required PK samples and post dose vital signs as outlined in the study schedule of events in [Appendix 1](#).

In addition to receiving study medication (AMG 714 or placebo), all subjects will be required to consume either placebo gluten or active gluten administered in a single-blind fashion. Beginning on the day following Visit 1 (i.e. Week 0/Day 1, since Visit 1 is defined as Week 0/Day 0) through Visit 2 (Week 2/Day 14), all randomized subjects will consume placebo gluten, in the form of gluten-free foodstuffs (e.g. rusks) provided by the Sponsor, twice a day (BID) at the time of two regularly consumed gluten-free meals (chosen by the subject). Starting at Visit 2, subjects will switch to consume a daily total of approximately 2-4g of active gluten, provided in the form of foodstuff identical in appearance to that provided during the two-week single-blind placebo-gluten period. These gluten-containing foodstuffs, supplied by the sponsor, will be consumed in approximately 1-2g doses BID at the time of two regularly consumed gluten-free meals (as chosen by the subject) from Visit 2 (Week 2/Day 14) through the end of the treatment period at Visit 7 (Week 12/Day 84). Consumption of additional products containing gluten will be prohibited and subjects will be expected to continue total adherence to their former GFD from the time of screening until the follow-up study visit (Visit 8, Week 16/Day 112).

Subjects' adherence to GFD and consumption of provided gluten will be periodically assessed via stool and urine sample testing using the iVYELISA GIP stool and urine gluten tests. Subjects with known or suspected GFD transgressions or those suspected of non-compliance to protocol specified gluten dosing will be counselled and allowed to continue in the study.

A study site staff member will contact each subject by telephone both one day and one week after the first study drug administration in order to assess for AEs. Subjects will return to the clinic every two weeks for study drug administration and/or efficacy and safety assessments as indicated in the study schedule of events in [Appendix 1](#). The final study drug administration will occur at Visit 6 (Week 10/Day 70). An end-of-study efficacy assessment

will be collected at Visit 7 (Week 12/Day 84). A final study visit will be conducted six weeks after the last administration of study drug at Week 16 (Visit 8/Day 112).

Subjects who meet all other study entry criteria will undergo upper gastrointestinal endoscopy and biopsy prior to baseline (Visit 1, Week 0/Day 0) and at the end of the 12-week randomized period while still on the gluten challenge within five days before Visit 7 (Week 12/Day 84) in order to assess changes from baseline in VH:CD ratio, IELs, and Marsh score.

If the screening biopsy shows villous atrophy with a VH:CD less than 1.5 (1.4 or lower), and after notification to the sponsor, the subject may be allowed to stay in the study but the gluten challenge will not be started (or will be interrupted if the patient has been started in the challenge) and the subject will be analysed separately for the main efficacy assessments (primary and secondary endpoints). Subjects with VH:CD 1.5 or above will receive the gluten challenge.

[figure not shown]
The threshold of VH:CD to receive gluten challenge was initially 2 (protocol version 1) and subsequently 1.8 (protocol version 2) before the final threshold of 1.5 VH:CD was adopted in protocol version 3. The population of subjects who received gluten challenge and had pre/post biopsies, a majority of the patients, will represent the per protocol population 1 (PP1) and will be analysed for the primary and secondary endpoints separately from the subjects who did not receive gluten challenge and had pre/post biopsies, a small fraction of the subjects who will represent the per protocol population 2 (PP2). All primary and secondary endpoints will be analysed in PP1 and PP2 separately.

All subjects will complete the BSFS at the time of each bowel movement from baseline (Visit 1, Week 0/Day 0) up to the final study visit (Visit 8, Week 16/Day 112). Subjects will complete the CeD PRO daily from baseline up to the final study visit. Subjects will also complete the GSRS at screening and, thereafter, weekly from baseline through the final study visit. The BSFS, GSRS and CeD PRO will be completed using a handheld electronic diary at times specified in [Appendix 1](#).

Safety will be monitored on an ongoing basis and subjects may undergo unscheduled visits for safety reasons, if needed. Safety will be assessed throughout the study by clinical laboratory tests, physical examination, vital signs, and AE monitoring.

[Figure 1](#) represents a schematic drawing of the study periods and visits.

Figure 1 CELIM-NRCD-001 study schematic

4 Randomisation

Randomisation, i.e. the random allocation of treatments to subject numbers, will be performed according to the design of the study. A detailed description of the randomisation method, including the size(s) of randomly permuted blocks used to balance the randomisation, will be stored at the restricted area of StatFinn server, where only the randomisation expert and the unblinded statistician will have access to. Once the data base is locked and the treatment code open, the randomisation documents will be moved to the non-restricted area.

Subjects will be randomized at a 1:1:1 allocation to receive 150 mg AMG 714 or 300 mg AMG 714, or placebo once every two weeks for a total of six administrations over ten weeks. Randomization will be stratified by site and sex.

5 Statistical hypotheses

The primary endpoint of the study is the difference in the Baseline-to-Week-12 % change of VH:CD ratio between each of the two AMG 714 dose arms against the placebo arm.

The primary endpoint will be tested for each of the two dose levels, 150 mg or 300 mg, separately as follows:

$H_{10}: \mu_{AMG\ 714\ (300mg)} = \mu_{Placebo}$
against the alternative

$H_{11}: \mu_{AMG\ 714\ (300mg)} \neq \mu_{Placebo}$
and

$H_{20}: \mu_{AMG\ 714\ (150mg)} = \mu_{Placebo}$
against the alternative

$H_{21}: \mu_{AMG\ 714\ (150mg)} \neq \mu_{Placebo}$

where $\mu_{AMG\ 714\ (300mg)}$, $\mu_{AMG\ 714\ (150mg)}$ and $\mu_{Placebo}$ denote the mean Baseline-to-Week-12 % change of VH:CD ratio in the high dose, low dose and placebo arm, respectively. Each of the two hypotheses will be tested using a two-sided, 0.05 level of significance without any adjustments for multiple comparisons.

6 Estimation of sample size

The sample size of approximately 63 subjects (21 subjects/arm) has been calculated to achieve at least ~ 80% power in the primary endpoint, the difference in the Baseline-to-Week-12 %-change of VH:CD ratio between the two AMG 714 arms and the placebo arm. This sample size provides close to 90% (88.8%) power to detect a 40-point difference between the placebo arm and the 300mg high-dose arm, and close to 80% (79.3%) power to detect a 35-point difference between the placebo arm and the 150mg low-dose arm.

This sample size calculation is based on the following assumptions:

- Two-sided type one error rate $\alpha = 0.05$.
- Power $1-\beta = 80\%$.
- Analysis method: one-way ANOVA by SAS® (proc power).
- Common SD = 36 for the baseline to Week 12 %-change in VH:CD.
- 45%-change (decrease) in the placebo group, %-change (decrease) of 10% in the 150mg and 5% in the 300mg arms.
- Drop-out rate ~19% (assuming non-evaluable drop-outs plus DH $\leq 15\%$ and non-evaluable due to technical issues or villous atrophy at baseline $< 5\%$).

These assumptions are based on the observations made in a similar 12-week gluten challenge study done with 3-5 grams of gluten per day (Lähdeaho *et al*, 2011). According to this sample size calculation (including a 19% drop-out rate), 17 completed evaluable subjects/arm (51 subjects in total) will be needed for the primary analysis.

7 Statistical methods

7.1 Data sets to be analysed

The populations for analysis will be the intention to treat (ITT, safety population, at least one dose of the investigational product received) and the per protocol populations (PP, efficacy, i.e., available and evaluable pre- and post-biopsy information [Week 6]).

PP population: the PP population will exclude non-evaluable subjects and subjects with major protocol deviations thought to impact the ability to assess the effect of treatment. Exclusion of subjects from the PP set will be reviewed, documented and approved before the study is unblinded to the study Sponsor. There will be two PP populations, PP1 (including subjects who received gluten challenge for at least a week) and PP2 (including subjects who did not receive gluten challenge, or received gluten challenge for less than a week).

Non-evaluable subjects are pre-specified before database lock and will include subjects dropping out of the study before Week 6 (insufficient duration of the gluten challenge and/or no exit biopsy).

Major protocol deviations will be examined by the Sponsor prior to database lock and the decision to include or exclude subjects from PP population based on the protocol deviations will be documented.

Sensitivity analyses may be conducted, if deemed necessary, for protocol deviations such as:

1. Intake of any forbidden concomitant medication or participation in other medical procedures, in case there is reason to believe, by the judgement of the Sponsor or investigator, that such concomitant medication/procedures had a significant effect on the efficacy data obtained. For example, analgesics/anti-diarrheals which may affect symptoms;
2. Significant deviations from the inclusion/exclusion criteria or study conduct., including, but not limited to, subjects who missed one or more doses of study drug, were not fully compliant with the gluten challenge, or had dermatitis herpetiformis.

ITT population: this population consists of all randomized subjects who have received at least one dose of the study drug. Subjects will be analyzed in the treatment group to which they are randomized. Safety population is by definition the same as the ITT population. If a subject had a misallocated treatment on a specific visit observed upon unblinding, a secondary sensitivity analyses will be performed on an as treated basis.

The primary and secondary endpoints as well as exploratory an PD variables will be analysed using the two PP populations. Demographic and baseline variables will be assessed using both ITT and PP populations. Safety parameters will be analysed using the ITT population. Compliance data will be reviewed to assure subjects were treated as randomized.

A detailed description of the study populations and subjects included will be given in the Subject Classification Document, which will be finalized before the database lock.

Table 1 Data sets to be used in the analysis

Primary variable	Secondary variables	Exploratory/PD variables	Safety variables	Demographic and baseline variables
PP*	PP*	PP*	ITT	ITT PP*

*PP population includes PP1 and PP2 populations.

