7.2.3 Handling of data from discontinued subjects

Subjects who are randomized but discontinue before receiving study treatment will not be included in any efficacy or safety analysis, but will be included in the disposition of subjects table. Subjects who receive at least one dose of study treatment will be included in ITT analysis population.

Subjects discontinuing from study drug administration before Week 6 will be excluded from the PP analysis populations and the second biopsy will not be collected. Subjects discontinuing on or after Week 6 will be included in the PP analysis population sets if the second biopsy can be collected (in the case a subject is lost to follow-up on or after Week 6 and a biopsy cannot be collected, the subject is considered non-evaluable and excluded from the PP populations).

Subjects will be considered study completers at Visit 7 (Week 12/Day 84), regardless of whether or not the Final Study Visit (Visit 8; Week 16/Day 112) is attended.

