7.8.2 Clinical laboratory tests

Clinical laboratory tests include haematology, clinical chemistry, and urinalysis panels. The complete list of clinical laboratory parameters is presented in Table 3 below.

Table 2 Clinical laboratory tests

Haematology	Clinical Chemistry	Urinalysis
Basophils (% and absolute)	Alanine Aminotransferase (ALT)	Blood Cells (Erythrocytes, Leukocytes)
Eosinophils (% and absolute)	Albumin	Glucose
Haematocrit	Alkaline Phosphatase	Ketones
Hemoglobin	Aspartate Aminotransferase (AST)	Microscopic evaluation
Lymphocytes (% and absolute)	Bilirubin (Total)	Protein/Albumin
Monocytes (% and absolute)	Blood Urea Nitrogen (BUN)	
Neutrophils (% and absolute)	Calcium	
Platelet Count	Chloride	
Red Blood Cell (RBC) count	Creatinine	
White Blood Cell (WBC) count	Glucose	
	Lactate dehydrogenase (LDH)	
	Potassium	
	Protein (Total)	
	Sodium	

Clinical laboratory parameters will be obtained at times indicated in the study schedule ([Appendix 1](#)). Blood and urine samples collected at the Screening Visit will require a minimum 8-hour fast.

All clinically significant findings during the study should be followed until resolution or until the finding is clinically stable. Subjects may be withdrawn from study drug if the Investigator or Sponsor deems the clinically significant finding compromising to the subject's safety; however, these subjects will continue to be followed-up per protocol, unless consent is withdrawn.

Detailed information regarding the collection and handling of clinical laboratory specimens, including blood draw totals for each visit and instructions for re-testing of missing or compromised specimens, can be found in a separate Specimen Collection and Processing Manual or equivalent document supplied by the Sponsor.

Laboratory test values will be presented by individual listings with flagging of values outside the normal ranges (normal ranges will be presented in statistical analysis report appendix). Absolute laboratory values and changes from baseline will be presented using summary statistics by treatment group and visit. Clinical laboratory variables will also be explored in individual and mean curves. ITT analysis population will be used.

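### Antibody and symptom endpoints need no biopsy but are modelled and summarised only in the biopsy-based per-protocol sets; add one supportive as-randomised analysis

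*SAP*

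**What the plan says.** SAP Section 7.1 sets the population for everything except safety and baseline: "The primary and secondary endpoints as well as exploratory an PD variables will be analysed using the two PP populations". Table 1 says the same, and the paragraphs on anti-tTG, anti-DGP, BSFS, GSRS and CeD-GSRS (Section 7.6.2) and on CeD PRO (Section 7.7.4) each repeat it.

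Membership of PP depends on the biopsy. Section 7.1 asks for "available and evaluable pre- and post-biopsy information" and also removes major deviators. Drop-outs before Week 6 are non-evaluable because of "insufficient duration of the gluten challenge and/or no exit biopsy". Section 7.2.3 adds two rules:

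- "Subjects discontinuing from study drug administration before Week 6 will be excluded from the PP analysis populations and the second biopsy will not be collected".
- For loss to follow-up on or after Week 6, where "a biopsy cannot be collected, the subject is considered non-evaluable and excluded from the PP populations".

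The ITT set (all randomised and dosed, analysed as randomised) is defined in Section 7.1. It is used for safety, for baseline data and, under Section 7.2, for listings.

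**The concern.** Antibody results come from blood and the symptom scores from an electronic diary. A missing or unreadable exit biopsy leaves both intact. Excluding the whole subject discards usable data and makes the comparison depend on events after randomisation: stopping drug, leaving without a biopsy, deviating from protocol. Treatment or gluten-induced symptoms can influence each of these, so the arms compared are no longer fully the randomised arms. The models planned for these endpoints are repeated-measures models that can use partial follow-up, so the exclusion is not technically needed. The SAP itself recognises the distinction: Section 7.2.2 limits last-observation-carried-forward to variables that depend on the biopsy. Table 1 draws no such line.

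**Working it through.** **Inputs.** Section 6: 63 randomised, 51 evaluable, about 19% loss, SD 36. Section 7.6.2: serology modelled at Visits 3, 5, 7 and 8; GSRS and CeD-GSRS at Weeks 1 to 16. Section 3: visits are two-weekly from Week 0 to Week 12 and then at Week 16, so these serology visits are Weeks 4, 8, 12 and 16; active gluten starts at Week 2.

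**1. The plan's own figures.** One-way ANOVA contrast, 17 per arm, 51 − 3 = 48 error degrees of freedom, two-sided 0.05. The standard error is 36 × √(2/17) = 12.35. Noncentrality is 40/12.35 = 3.24, giving 88.8% power, and 35/12.35 = 2.83, giving 79.3%. Both match Section 6. The loss is 63 − 51 = 12, and 12/63 = 19.0%. There is no arithmetic error.

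**2. What the 12 is.** Section 6 pools drop-outs plus dermatitis herpetiformis (at most 0.15 × 63 = 9.45) with technical failures or baseline atrophy (under 0.05 × 63 = 3.15). Dermatitis herpetiformis is only a possible sensitivity topic in Section 7.1. Subjects with baseline atrophy and both biopsies go to PP2 (Section 3). Deviation exclusions are not quantified. The 12 is therefore not a count of PP exclusions.

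**3. Does the stated reason reach each group removed?**

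- *Leaves the study before Week 6:* yes. Gluten exposure is under 6 − 2 = 4 weeks.
- *Lost on or after Week 6 without a biopsy, or biopsy technically unusable:* no. If challenged from Week 2 and still on it at Week 6, exposure is about four weeks or more. A missing biopsy does not bear on these endpoints.
- *Stops drug before Week 6 but stays in follow-up:* uncertain. Section 7.2.3 excludes on stopping drug, whereas Section 7.1 refers to dropping out of the study. Section 7.8.2 says of subjects withdrawn from drug for a laboratory finding: "however, these subjects will continue to be followed-up per protocol, unless consent is withdrawn". Whether diaries and serology continue depends on the protocol.
- *Major deviation:* a separate reason is given in Section 7.1.

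**4. Modelled post-baseline results left unused per excluded subject.**

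| Course | Each antibody (of 4) | GSRS weeks (of 16) |
|---|---|---|
| Leaves just before Week 6 | 1 | 5 |
| Lost just after Week 6, no biopsy | 1 | 6 |
| Lost just after Week 8, no biopsy | 2 | 8 |
| Unusable biopsy, followed to Week 16 | 4 | 16 |

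**5. Scale only, assuming 12 exclusions.** Planned totals are 63 × 16 = 1,008 GSRS scores and 63 × 4 = 252 results per antibody. If all 12 leave just before Week 6, the unused share is 60/1,008 = 6% and 12/252 = 5%. If all 12 are followed to Week 16, it is 192/1,008 = 19% and 48/252 = 19%. Neither is an estimate, because the true number is unknown.

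**6. Is the gap filled elsewhere?** Section 7.1 offers deviation analyses only as an option: "Sensitivity analyses may be conducted, if deemed necessary, for protocol deviations such as". Its as-treated analysis concerns misallocated treatment. The Section 7.9 analyses are optional and may be limited to histology. Section 7.2 gives ITT listings. None fixes an as-randomised comparison of these endpoints.

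**The case against.** The population choice is explicit and consistent, and it is protected by blinding: "Exclusion of subjects from the PP set will be reviewed, documented and approved before the study is unblinded to the study Sponsor". The endpoints concern attenuation of gluten-induced effects, so a subject with little gluten exposure says little about them. Deviation exclusions have their own rationale, namely deviations judged to impair assessment of the treatment effect. Section 7.1 gives anti-diarrhoeals as an example of a medication that can distort symptoms.

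Selection is also not hidden. Section 7.3 tabulates discontinuations and their reasons, population counts and major deviations by arm. Section 7.4 gives baseline data in both ITT and PP. Section 7.8.1 tabulates adverse events by arm and by challenge period, and these are analysed in ITT.

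Most of this stands. Early leavers and deviators are excluded for stated reasons, and a reader who inferred that the SAP gives none would be wrong. Blinded approval prevents selection by known arm, but it does not undo selection on post-randomisation events. The disposition and baseline tables show how much selection occurs and why, but not what it does to the antibody and symptom comparisons. None of these arguments covers the subject with adequate challenge whose only defect is the biopsy.

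**Conclusion.** The point holds as a cheap improvement to secondary and exploratory analyses. The firm part is subjects lost on or after Week 6 without a biopsy, or with an unusable one: their antibody and diary data are dropped for a reason that does not bear on those data. Subjects who stop drug early but remain in follow-up may be a second such group, if the protocol keeps collecting these data. For early leavers and deviators the exclusion is reasoned, but it is still selection after randomisation.

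Three stronger readings are tempting, and the document does not support them:

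- *That 12 subjects (19%) will lose usable data.* The 12 is a pooled allowance for the biopsy endpoint.
- *That the results will be biased towards the drug.* Neither the direction nor the size of any bias can be derived from the SAP.
- *That the primary result is affected.* VH:CD change needs both biopsies, and the trial is powered on it alone.

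**What to change.** Keep PP1/PP2 as planned. In Table 1 and in the sections on serology, BSFS, GSRS, CeD-GSRS and CeD PRO, add one pre-specified supportive analysis:

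- **Set:** the existing ITT population, as randomised, using all available repeated measures. State the missing-at-random assumption for subjects who leave.
- **Grouping:** by whether the screening VH:CD qualified the subject for the gluten challenge under the protocol version in force (Section 3 records thresholds of 2, then 1.8, then 1.5). Do not group by challenge actually received. Gluten starts at Week 2, so someone leaving before then would be pooled with baseline-atrophy subjects because of a post-randomisation event.
- **BSFS:** the weekly count model has no exposure term, so use complete weeks only or a log(days observed) offset in this analysis.

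The cost is SAP wording and extra tables from data already collected. Early leavers had little gluten exposure (none before Week 2, under four weeks before Week 6) and may dilute the estimates; the PP result alongside makes this visible. Week 12 stays missing for those who leave, so the estimate rests on the stated assumption.
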